## 7.2.3 Histopathology and Molecular Assay documentation

The documentation of histopathologic and molecular assays will be accomplished by use of standard laboratory and pathology methods and commercially available assay kits suitable and designated for research. The results of the documentation (i.e. slide serial and catalogue numbers and assay results) shall be recorded in the Histopathology and Molecular Assay log (see appendix D).

## 7.2.4 Subject Subjective Assessments

## 7.2.4.1 Level of discomfort/pain

Treatment associated level of discomfort/pain experienced by the subjects will be measured on a 10cm Visual Analogue Scale (VAS) were 0 cm is 'no pain' and 10 cm is 'intolerable pain'. The subjects will be given a VAS and be asked to mark their perception of discomfort/pain immediately following each treatment (see appendix E)

## 7.2.4.2 Level of improvement and satisfaction

Subject's Improvement and Satisfaction with treatment will be recorded by using the GAI scale at the last follow up visit (see Appendix B).

Table 1 - Clinical Evaluation Tools

Claim/task	When to conduct?	Tool		
Photography	Baseline, immediately before	Standardized digital photographs		
	treatments 2, 3, FU 3			
Vaginal pH	Baseline, immediately before	Standard pH paper		
	treatments 2, 3, FU 3			
Histopathology & Molecular	Baseline, immediately before	Histology slides, special staining		
Studies	treatments 2, 3, FU 3	and assays.		
Immediate and short term	Immediately following treatments	Examination of skin in the treated		
response evaluation by	1-3	area based on 5 level scale		
investigator		(Appendix F)		
Subject's duration of post-	Before treatments 2, 3, FU 3	Subject Questionnaire on post		
treatment adverse events questionnaire		treatment response (Appendix G)		
Subjects discomfort/pain	Immediately following treatments	VAS (Appendix E)		
assessment	1-3			
Subjects improvement/	FU3.	GAI (see Appendix B)		
satisfaction assessment				
score				
Independent reviewers score	At the end of the study	GAI (see Appendix B)		

Confidential 11

## 7.3 Screening Procedures

## 7.3.1 Subject Enrollment

If the subject has met the preliminary study criteria the study doctor, and/or his designee, will obtain an informed consent from the subject, clearly indicating her understanding of the requirements and possible risks involved with study participation and other applicable treatment options.

During the first visit, the study investigator, and/or his designee, will screen the subject for eligibility to participate in the clinical study using the Inclusion, Exclusion criteria. During screening the study doctor will review the subject's medical history, and examine the subject's targeted area to ensure that it meets the study criteria. The subject will complete screening and the treatment will be scheduled. Treatment may be performed on the day the subject was enrolled or no later than one week following enrollment and screening. During the first visit, the investigator will ask women of child-bearing potential for the date of their last period, if not applicable the investigator shall inquire about the form of contraceptive they use to confirm they meet the inclusion criteria.

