#### 5.2.1 Inclusion Criteria

Subjects must meet all of the following inclusion criteria to be entered into the study:

- 1. Healthy female between the ages of 25 and 65.
- 2. Able to read, understand and voluntarily provide written Informed Consent.
- 3. Able and willing to comply with the treatment/follow-up schedule and requirements.
- 4. Fitzpatrick skin type I-VI.
- 5. Sexual activity (vaginal intercourse once per month) in a monogamous relationship.
- 6. Women of child-bearing age are required to be using a reliable method of birth control at least 3 months prior to study enrollment and have a negative Urine Pregnancy test at baseline.
- 7. Women requesting aesthetic benefit to the vaginal mons, introitus and labia.

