#### 5.2.2 Exclusion Criteria

Any of the following will exclude the subject from the study:

- 1. Pregnant or intending to become pregnant during the course of study. A urine pregnancy test will be given to women of childbearing potential and performed during initial visit.
- 2. Having any active electrical implant anywhere in the body, such as a pacemaker or an internal defibrillator.
- 3. Having a permanent implant in the treated area.
- 4. Prior use of retinoids in treated area within 2 weeks of initial treatment or during the course of the study.
- 5. Use of oral Isotretinoin (Accutane®) within 6 months of initial treatment or during the course of the study.
- 6. Patient on systemic corticosteroid therapy 6 months prior to and throughout the course of the study.
- 7. Prior skin treatment with laser in treated area within 6 months of initial treatment or during the course of the study.
- 8. Prior use of collagen, fat injections and /or other methods of skin augmentation (enhancement with injected or implanted material) in treated area within 4-6 weeks of initial treatment or during the course of the study. Treatment may not be performed at all over permanent dermal implants.
- 9. Prior ablative resurfacing procedure in treated area with laser or other devices within 12 months of initial treatment or during the course of the study.
- 10. Any other surgery in treated area within 12 months of initial treatment or during the course of the study.
- 11. History of keloid formation or poor wound healing in a previously injured skin area.
- 12. History of epidermal or dermal disorders (particularly if involving collagen or microvascularity).
- 13. Open laceration or abrasion of any sort on the area to be treated.
- 14. Active STD (e.g. genital Herpes Simplex, condylomata) or vaginosis; any tissue biopsy will be deferred or

Confidential 8

delayed to a later time point until the infection is resolved.

- 15. Chronic vulvar pain or vulvar dystrophy.
- 16. History of immunosuppression/immune deficiency disorders (including HIV infection or AIDS) or use of immunosuppressive medications.
- 17. Having any form of active cancer at the time of enrollment and during the course of the study.
- 18. Significant concurrent illness, such as uncontrolled diabetes i.e. any disease state that in the opinion of the Investigator would interfere with the treatment, or healing process.

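### Section 7.3.1 makes the contraception question a fallback, contrary to inclusion 6, and no pregnancy or contraception check is stated before Tx2 or Tx3

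*Combined protocol and SAP*

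**What the plan says.** **Eligibility criteria.** Inclusion 6 (section 5.2.1) reads: "Women of child-bearing age are required to be using a reliable method of birth control at least 3 months prior to study enrollment". The same item requires that they "have a negative Urine Pregnancy test at baseline". Exclusion 1 (section 5.2.2) bars women who are "Pregnant or intending to become pregnant during the course of study" and places a urine test at the initial visit for women of child-bearing potential. Inclusion 5 requires "Sexual activity (vaginal intercourse once per month) in a monogamous relationship".

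**Screening step.** Section 7.3.1 says that the investigator or designee "will screen the subject for eligibility to participate in the clinical study using the Inclusion, Exclusion criteria". Later in the same paragraph, "the investigator will ask women of child-bearing potential for the date of their last period", and then: "if not applicable the investigator shall inquire about the form of contraceptive they use to confirm they meet the inclusion criteria". Treatment may follow on the day of enrolment or up to one week later.

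**Later visits.** Sections 5.1 and 7.1 schedule three treatments about four weeks apart, and section 7.5 includes an internal vaginal treatment in each session. Table 1 (section 7.2.4.2) and the flow chart in Appendix A list the assessments by visit. Neither has an entry for a pregnancy test, a last-period question or a contraception question at any visit. Appendix A marks eligibility assessment at Visit 1 only.

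**The concern.** The second half of the 7.3.1 sentence gives its own purpose, which is to confirm the inclusion criteria. Its condition sends the contraception question to women for whom a last-period date does not apply. Women who can give a date are, in general, the ones still menstruating and therefore the ones for whom inclusion 6 matters most. The date tells staff nothing about contraceptive use over the preceding three months.

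The second difficulty is time. Exclusion 1 refers to the course of the study, inclusion 5 makes intercourse a condition of entry, and treatment is repeated twice after the only stated test. The protocol does not say how the criterion is confirmed at those two sessions.

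At stake are subject safety and consistent application of the entry criteria. No sample-size, power or other statistical figure depends on this point.

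**Working it through.** The plan gives no figure to reproduce. The check compares passages and then does simple day arithmetic.

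**Step 1: who must use contraception, and who is asked.**

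| Woman of child-bearing potential | Inclusion 6 applies? | Asked for last-period date (7.3.1)? | Asked about contraception under that sentence? |
|---|---|---|---|
| Gives a last-period date | Yes | Yes | No |
| Date does not apply | Yes, if of child-bearing age | Yes | Yes |

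The first row is the conflict: the criterion applies, but the specific step for confirming it is skipped.

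**Step 2: what still covers Tx1.** Two provisions do not depend on the last-period answer. One is the baseline urine test (inclusion 6 and exclusion 1). The other is the general screen against all criteria in 7.3.1.

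**Step 3: time from the single test to each treatment.** Inputs:
- test at the initial visit (exclusion 1)
- 0 to 7 days from screening to Tx1 (7.3.1)
- four weeks, or 28 days, between treatments (5.1, 7.1), taken as exact although 7.1 calls the interval approximate

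Formula: days from test to Tx*k* = (0 to 7) + 28 × (*k* − 1).
- Tx1: 0 to 7 days
- Tx2: 0 + 28 = 28 to 7 + 28 = 35 days
- Tx3: 0 + 56 = 56 to 7 + 56 = 63 days

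**Step 4: search for a later check.** Neither Table 1 nor Appendix A has one. The nearest item is the concomitant-medication row in Appendix A, marked at all four visits, which might pick up a drug-based contraceptive incidentally. Section 9.1.3 counts a congenital anomaly or birth defect as a serious adverse event, so the plan recognises the outcome. Section 10.4 does not name pregnancy among its possible reasons for withdrawal.

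**Step 5: baseline test in the flow chart.** Sections 5.2.1 and 5.2.2 both require it. Appendix A gives it no row.

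**The case against.** The strongest reply is that the last-period sentence is an additional question and does not replace the eligibility screen. The same paragraph requires every subject to be screened against all criteria, inclusion 6 is mandatory whatever that sentence says, and the urine test is unconditional. This stands, and it settles Tx1. A reader might infer from the wording that menstruating women enter treatment with no pregnancy check at all; the documents do not support that. What the reply leaves untouched is that the one instruction on how to confirm contraception points staff away from the women concerned.

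A second reply is that "using a reliable method of birth control at least 3 months prior to study enrollment" may mean a minimum duration of continuing use, so a reader should not conclude that the requirement lapses at enrolment. That reading is open. The text states nothing explicit for the period after enrolment, and the ambiguity is itself a reason to clarify it. The consent text was not available for this review, so what subjects are told about contraception during the study cannot be judged.

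A third reply is that the eligibility row at Visit 1 in Appendix A includes the urine test by reference. That is fair and makes the missing row minor. It does not help for Visits 2 and 3, where eligibility is not marked.

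**Conclusion.** The point holds in two parts. First, the condition in 7.3.1 conflicts with inclusion 6. Second, exclusion 1 refers to the course of the study, but no check is stated before two of the three treatments, which fall 28 to 35 and 56 to 63 days after the only planned test. The omission of the baseline test from Appendix A is a smaller inconsistency. The intervals assume exact four-week spacing and a test on the day of screening.

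Two further inferences are tempting and should not be drawn. One is an expected number of pregnancies. The documents give no contraceptive failure or conception rates, the sample in section 8.2 is 10, Appendix I makes expansion to 300 subject to IRB review, and ages run to 65, so not every subject is at risk. Nor would a failure rate among contraceptive users measure the defect in 7.3.1. The other is that an undetected pregnancy would distort the pH or tissue results; nothing in the documents supports that.

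This is a safety and eligibility inconsistency that is clear on the page and nearly free to correct.

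**What to change.** 1. **Section 7.3.1:** delete the condition, so that the last-period question and the contraception question both go to every woman of child-bearing potential.
2. **Appendix A:** show the already required baseline urine test at Visit 1.
3. **Sections 5.2.1, 5.2.2 and 7.3.1 and Appendix A:** reconcile them so that the protocol states how exclusion 1 is confirmed before Tx2 and Tx3, and whether inclusion 6 continues after enrolment. Which clinical rule applies, and by what means it is checked, is for the sponsor and the investigator to decide.

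The cost is protocol wording, one flow-chart entry and a few questions per subject. Items 1 and 2 add no test beyond the one already required. Any cost under item 3 depends on the rule chosen.

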## 7.3.2 Subject Identification

At enrollment, each subject will receive a unique identifying number that will be composed of a consecutive number and her initials. This unique identifier will be used throughout the entire study and will be entered in the subject's CRF for each treatment and photographs.

#### 7.4 Pre-Treatment Procedures

#### 7.4.1 Subject Skin care and medication

- Before attending the first treatment, the subject will shave the treatment area at home, using foam or gel to minimize skin irritation.
- Apply medical Grade Glycerin on the treated area

## 7.4.2 Photography

#### 7.4.2.1 Photography

Photographs will be taken prior to treatment and throughout the study according to specified time points detailed in Table 1, utilizing standard scientific equipment.

The photos should be taken in a private room or area of the clinic under controlled conditions, including the distance, angle, background and lighting in order to achieve high-quality before & after sets. Do not use direct illumination. The subject should be placed in the same position each time. As each photograph is taken, it should be viewed to ensure that it is in focus and is similar to its baseline counterpart in all technical aspects, including lighting, distance and angle.

For consistency purposes, the same person should ideally take all study photographs, especially per subject. The digital files should follow a consistent standard naming scheme, for example: 001TM\_Tx1\_Mons Pubis.

#### 7.5 Treatment

All patients will receive treatment of the mons pubis, labia and vaginal introitus with the Freeze Diamondpolar

Confidential 12

Protocol: CS2815v4 Approval Date:

Approval Number: IRCM- Continuing Review Date: February 24, 2017

applicator. Patients will also receive an internal vaginal treatment with the investigational handpiece/applicator.

A dedicated Freeze Diamondpolar applicator will be used for each patient. Each applicator will be clearly labeled with the name of the patient. The patient will take the applicator or disposable head with her at the end of the first treatment session (Tx1) and will bring it back to the clinic for each of the additional treatment sessions (Tx2 and TX3). The applicator should not stay in the clinic possession during the study period. At the end of the study the applicators will return to Venus Concept.

The internal vaginal system consists of an the handheld applicator and disposable cover. The applicator contains 3 pairs of electrodes that deliver the Multi Polar Radiofrequency (RF) and Pulsed Magnetic Fields (PEMF) energy contained in a plastic housing with thermal sensors for detecting the tissue temperature. The disposable cover comes in 2 sizes to accommodate patient sizes.

Based on the mild nature of treatment, anesthesia is not required. Treatment procedure should include positioning of the patient in a manner that enables comfortable access to the treated anatomical site. The positioning of subjects during treatment will be contingent on the location of the treated anatomical site. The following steps should be followed in each treatment session:

- 1. Set the treatment parameters (see Venus Versa (MP) User Manual for the Diamondpolar applicator ). Set the desired energy level between 10%-35% according to the skin type, severity of the treated condition, treatment area, etc. Set conservative parameters for the first treatment, and then gradually increase during treatment or in subsequent treatments according to desired impact, patient's comfort, AEs and results.
- 2. External treatment consists of a multiple passes over the treatment area with treatment parameters adjusted according to patient's comfort and temperature measurements by an external thermometer.
- 3. Move the applicator over the treated area, to maintain a temperature of 40°C-42°C when treating the labia area and 40°C-45°C when treating the monspubis.

#### 7.6 Post-treatment Instructions

### 7.6.1 Post treatment care

- 1. Transient skin erythema and edema, as well as heat or tingling sensations, may last up to a few hours after the treatment, but typically no longer. In the event of post-treatment discomfort, it is recommended to cool the treated area immediately following treatment with air cooling. Cold packs (not frozen) may also be placed on the treated area.
- 2. During the day following treatment, care should be taken to prevent trauma to the treated site: avoid hot baths, massage, contact sports, swimming etc. The skin should be kept clean to avoid contamination or infection; any mechanical or thermal damage to the area must be avoided.

## 7.7 Follow-up regimen

Follow-up visits will be combined with treatments visits 2 and 3 and an additional follow up visit will occur one month (± seven days) after the last treatment as detailed in Appendix A.

### 8 Study Analysis Plan

## 8.1 Study Hypothesis

The study will confirm that the Freeze Diamond Polar applicator is safe for the treatment of the mons pubis, vaginal introitus and labia, and will result in improvement in skin laxity and skin irregularities.

The study will also confirm that the investigational applicator is safe for internal treatment of the vagina.

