## **Study Synopsis**

	· · · ·				
Study Title	Clinical evaluation of the safety and Efficacy of using Multi-Polar RF and PEMF technologies for the treatment of the Mons Pubis, Vaginal Introitus and Labia Skin Laxity				
Protocol No:	CS2815				
Device Name:	Modified Venus Versa (MP)  device with Freeze Diamondpolar and Investigational Applicators				
Design	Feasibility, single-center, baseline-controlled, prospective study				
Projected Study period	Initiation Date: February 2016 Completion Date: February 2017				
Objectives	
 
Primary objectives
 
To evaluate the safety of treating the mons pubis, labia and vaginal introitus with the Freeze Diamond Polar applicator.
 
To evaluate the safety of the internal treatment of the vagina with an investigational applicator
 
To verify the efficacy of using the Freeze Diamond Polar applicator for improving general skin appearance of the mons pubis, vaginal introitus and the labia including improvement of skin irregularities and skin laxity.
 
To determine and/or quantify any potential regenerative properties associated with the study treatments.
 
Secondary objectives
 
To evaluate subject's assessment of comfort and pain associated with treatments.
 
To evaluate subject's satisfaction with treatment results and assessment of improvement.
 
To determine if any regenerative properties are associated with the
 
				
Hypothesis	
 
Mons pubis, Vaginal Introitus and the Labia.
 
The study will confirm that the Freeze Diamondpolar applicator is safe for treating the mons pubis, labia and vaginal introitus which will result in improvement in general skin appearance including an improvement in skin irregularities and skin laxity.
 
The study will confirm that the investigational applicator is safe for
 
				
Study population	internal treatment of the vagina.  1 site with 10 subjects				
Main Inclusion Criteria	
 
Healthy female between the ages of 25 and 65.
 
Sexual activity (vaginal intercourse once per month) in a monogamous relationship.
 
Requesting aesthetic benefit to the vaginal mons, introitus and labia.
 
				

Confidential 2

Protocol: CS2815v4 Approval Number: IRCM-

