### 8.2 Sample Size Justification

The proposed study is a feasibility study for evaluating the safety and the efficacy of using the Freeze Diamond Polar applicator for treatment of the mons pubis, vaginal introitus and labia anatomical areas and the investigational applicator for treatment of the vagina. Based on previous experience with other RF devices, we believe that the proposed study sample of 10 subjects per each anatomical area (total of 10) will be sufficient to evaluate the safety and the efficacy of the treatment and to obtain qualitative assessments of comfort levels experienced during treatments.

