#### 8.3 Study Analysis

• An intermediate safety report based on qualitative analysis of immediate and short term reaction and on AEs will be produced based on analysis of data collected immediately post treatment number one of all the enrolled subjects. This data will be used to adjust further treatments parameter. The interim

Confidential 14

- reports will not affect the continuation of the study. The study will, regardless of the interim report results, be finalized according to this protocol.
- After FU3, the photographs will be sent to independent evaluators that will grade on a GAI scale the change in skin laxity according to photograph of FU3 compare to baseline. Descriptive statistics and correlations between variables will be performed on these results.
- After FU3 the subject assessment on the change in skin laxity on a GAI scale will be analyzed. These results will be correlated with the evaluation done by the independent evaluators in order to learn on the relationships between objective and subjective improvements assessments.
- After FU3 all data collected by response and discomfort/pain level (VAS) and the 5-level short term response scale results will be analyzed using descriptive statistics.
- After FU3, the vaginal pH values will be sent to the PI for formal data entry and analysis. These results will be correlated with the evaluation done by the independent evaluators in order to learn on the relationships between objective and subjective improvements assessments.
- After FU3, the histology slides and molecular assay results will be sent to the PI for formal data entry
  and analysis and archive storage (histology slides). These results will be correlated with the evaluation
  done by the independent evaluators in order to learn on the relationships between objective and
  subjective improvements assessments.

The study reports will provide information for use in research & development, and future planned studies. Descriptive statistics and correlations between variables will be performed.

Safety: Adverse events reported will be listed, documenting course, outcome, severity, and possible relationship to the treatment.

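### The hypothesis promises confirmation of safety and improvement, but an uncontrolled feasibility study of 10 with no interval, test or success criterion can give only preliminary estimates

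*Combined protocol and SAP*

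**What the plan says.** Section 8.1 sets out the hypothesis in two parts. For the external applicator: "The study will confirm that the Freeze Diamond Polar applicator is safe for the treatment of the mons pubis, vaginal introitus and labia", and treatment "will result in improvement in skin laxity and skin irregularities". For the internal applicator: "The study will also confirm that the investigational applicator is safe for internal treatment of the vagina". The synopsis carries the same hypothesis, and both the synopsis and Section 3.1 list verifying efficacy as a primary objective.

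The synopsis describes the design as "Feasibility, single-center, baseline-controlled, prospective study" and the population as "1 site with 10 subjects". Section 8.2 also uses the feasibility label and justifies the number from experience with other RF devices: "we believe that the proposed study sample of 10 subjects per each anatomical area (total of 10) will be sufficient". Sections 2 and 5.1 instead allow 10 to 300 subjects. Appendix I makes a study of up to 300 depend on IRB review of the first 10.

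On analysis, Section 8.3 says: "Descriptive statistics and correlations between variables will be performed". Adverse events are to be listed with course, outcome, severity and possible relationship to treatment.

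**The concern.** To confirm something, a study needs a criterion that a result could fail. Sections 8.1 to 8.3 give none: no acceptable event rate, responder definition, success threshold, test or confidence interval. The planned correlations relate one assessment to another and test neither safety nor improvement. No outcome of the study would formally contradict the hypothesis.

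What is at stake is how the results are read. Section 8.3 sends the reports to research and development and to future studies, and Appendix I puts the first 10 subjects' safety results before the IRB ahead of any expansion. An event-free series of 10, read against this hypothesis and shown without its upper limit, would look far more reassuring than it is.

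**Working it through.** **The plan's own figure.** Section 8.2 gives no alpha, power, effect size, event rate or margin, so N = 10 cannot be reproduced by any formula. The check is therefore what 10 subjects can support.

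**Inputs.** N = 10 in total (synopsis, 8.2). Subjects who do not complete are not replaced (5.1). GAI runs from -3 to +3 with 0 for no change (Appendix B). The event rates, the true improvement rates and the 50% null below are assumptions, because the documents give none.

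**Safety: upper limit after zero events.** The exact limit is 1 - a^(1/n), with a = 0.05 one-sided and a = 0.025 for a two-sided 95% interval.

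- n = 10: 1 - 0.05^(1/10) = 25.9%; 1 - 0.025^(1/10) = 30.8%.
- n = 9, if one subject contributes no data: 28.3% and 33.6%.
- n = 300: 0.99% and 1.2%.

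**Safety: chance of seeing no event in 10 subjects, (1 - p)^10.**

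| Assumed true rate | Probability of no event |
|---|---|
| 1% | 90% |
| 5% | 60% |
| 10% | 35% |
| 20% | 11% |

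For scale, a one-sided 95% upper limit below 10% with no events needs ln(0.05)/ln(0.9) = 28.4, so 29 subjects. A limit below 5% needs 59.

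**Improvement: precision.** Clopper-Pearson 95% limits for r of 10 are the 0.025 quantile of Beta(r, 11 - r) and the 0.975 quantile of Beta(r + 1, 10 - r). For 7 of 10 improved this gives 35% to 93%; for 9 of 10, 55% to 99.7%.

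**Improvement: what a test could have shown.** Take a two-sided sign test with ten non-zero scores and a null of 50%:

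- 8 of 10: 2 x (45 + 10 + 1)/1024 = 0.109.
- 9 of 10: 2 x (10 + 1)/1024 = 0.021.
- 10 of 10: 2 x 1/1024 = 0.002.

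The chance of reaching 9 or more of 10 is 38%, 74% and 91% at assumed true improvement rates of 80%, 90% and 95%. Ten subjects could therefore exclude chance if the response were nearly universal. The plan contains no such test, and without a concurrent control a significant result would show change from baseline, not its cause.

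**The case against.** The strongest defence is that this is a self-declared feasibility study whose reports serve development and later studies, so *confirm* merely states what the sponsor expects. That is partly right. The design is acceptable for feasibility, and no analysis in 8.3 depends on the word. But the feasibility label argues for changing the hypothesis, because the two describe different kinds of study.

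Several stronger readings are tempting, and the documents do not support them.

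- A reader might infer that 10 subjects cannot show improvement at all. The sign-test figures say otherwise.
- A reader might infer that improvement is never compared with no change. It is: the GAI is a change score anchored at 0, and evaluators grade FU3 against baseline. What is missing is an interval or test on that score.
- A reader might infer that the plan directs an event-free series or a positive mean GAI to be reported as confirmation. Section 8.3 has no such rule, and Appendix I places IRB review before expansion.

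It can also be said that Sections 2 and 5.1 allow 300 subjects, where zero events would leave a two-sided limit of 1.2%. But only 10 is justified in 8.2, and Appendix I holds 300 back until the first 10 are reviewed. Even at 300, confirmation would need a stated threshold.

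**Conclusion.** The point holds as a mismatch between claim and design. It does not invalidate the study. For safety, N = 10 is decisive: an event-free result is compatible with true rates up to 30.8% (two-sided 95%), and an assumed 10% harm would be missed about one time in three. For improvement, the gap is the absent interval or test, the absent criterion and the absent control, with small N a secondary limit on precision.

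The limits rest on 10 evaluable subjects with independent outcomes. The 10% harm rate and the 50% null are illustrations, not figures from the plan. The change is worth making before results go to the IRB or into planning, because it alters what may be concluded from them.

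**What to change.** 1. Reword the hypothesis in 8.1 and the synopsis, the sufficiency statement in 8.2, and the efficacy objective in the synopsis and 3.1 as obtaining preliminary estimates. Editing 8.1 and 8.2 alone would leave the synopsis and 3.1 inconsistent with them. State that safety will not be called confirmed from the first 10 subjects.
2. In 8.3, report subjects with at least one device-related AE, burn or SAE as n/N with exact (Clopper-Pearson) 95% intervals, for the combined treatment session. Split by applicator or area only where the site of the event allows attribution. Both applicators are used in each session, the examination follows both (7.5), relatedness is to device or procedure (9.1.2), and Appendix F has no applicator field.
3. For mons pubis and labia, report the full evaluator GAI distribution at FU3, negative scores included, and the proportion with GAI of 1 or more with an exact 95% interval. These are the only areas on the evaluator form (Appendix C); the introitus has no box there. State in advance how several evaluators' scores are combined, for example by the median, and how a median between two categories is classified.
4. Reconcile the sample size of 10 (synopsis, 8.2) with 10 to 300 (Sections 2 and 5.1, Appendix I).

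The cost is a protocol amendment, a combination rule and a few exact intervals. No extra subjects or visits are needed. The downside is a less favourable stated claim.
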